4.4. Multicenter Study

Patients will be enrolled at approximately 486 investigational sites in approximately 27 different countries. To control for differences between sites and assure that treatment allocation is balanced within site, randomization will be stratified by site. Randomization blocks of size 4 will be dynamically allocated to sites. Patients will be assigned in a 1:1 ratio to the next available treatment (either dulaglutide 1.5 mg/week or placebo) from the block currently allocated to their site at the time the call was made to the IVRS. The number of patients randomized at each site in each country will be provided.

4.5. Patient Populations/Analysis Subsets

The patient populations and analysis subsets used in the study are described below.

Table 4.1. Analysis Population for REWIND

Population	Definition
All Entered	All patients who signed informed consents
All Randomized	All patients who were randomized to a treatment arm
Non-Randomized	All patients entered but not randomized to a treatment arm
Intent-to-Treat	All patients randomized within their treatment group regardless of whether or not they took study drug or correct study drug (same as all randomized population)
Per-Protocol	All patients in ITT and also meet the following criteria 
 • have not permanently discontinued study drug • no important protocol deviations • have completed the study • have an overall adherence with study drug of $\geq 75\%$

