4.2. General Considerations

All entered data will be verified, and archived at a contract research organization (CRO) external to Lilly and/or at Lilly. An independent statistical analysis center (ISAC) will perform analyses for the IDMC prior to unblinding. After database lock at the conclusion of the study, analyses for the major key manuscripts will be conducted by the same or another ISAC based on data supplied by the CRO and the relevant manuscripts will be prepared by a writing group chosen by the Operations Committee. Data listings, summaries, and analyses will also be performed by the CRO and/or by Lilly for the purpose of the final clinical study report (CSR).

Efficacy and safety analyses will be conducted using the intent-to-treat (ITT) population. This population will include all randomized patients within the treatment group the patients were assigned to regardless of whether or not they took study drug or the correct study drug. A patient is considered randomized once the call has been made to interactive voice response system (IVRS) and a treatment is assigned at Visit 3.

Additional analyses will be conducted using the per-protocol (PP) population. The PP population is a subset of the ITT population defined as all randomized patients who have not permanently discontinued study drug, discontinued from the study, have an overall adherence of $\geq 75\%$, and have no important protocol deviations. The primary efficacy analysis will be repeated using the PP population. Important protocol deviations are defined in Section 4.7.

The analysis populations used in this study are defined in [Table 4.1](#).

Unless otherwise specified, listings will be conducted using all randomized patients. The data collected will be presented as listings by investigator site, patient, and treatment.

Unless otherwise noted, all tests of treatment effects will be conducted at a 2-sided alpha level of 0.05 and CIs will be calculated at a 2-sided 95% confidence level. A graphical approach for multiple comparisons (Bretz et al. 2009; Bretz et al. 2011) will be used to strongly control the overall Type I error (2-sided alpha of 0.05) for testing the null hypothesis of no treatment effect with respect to the secondary endpoints.

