4.7. Important Protocol Deviations

Important protocol deviations will be listed for all randomized patients. The following protocol deviations will be considered important:

- not meeting any of the inclusion criteria [1], [6], and [9], or meeting any of the exclusion criteria [10], [11], [12], [13], and [21] (REWIND study protocol) that affect the primary endpoint analysis
- nonadherence to treatment regimen (that is, overall treatment adherence <75%)
- incorrect dispensation of study drug (patient received incorrect treatment)
- unblinding of treatment assignment for any reason
- using prohibited concomitant medications (that is, non-study GLP-1 analogs, pramlintide, or prescription weight loss drugs)
- safety laboratory or measures (calcitonin and/or serum creatinine and/or ECG) not taken for 18 or more months and study drug not discontinued

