4.11. Treatment Adherence

Treatment adherence will be assessed for each visit interval. Patients will be instructed to return any unused study drug syringes at each study visit for the purposes of study drug accountability. Study drug adherence will be calculated at each visit after baseline when study drug is dispensed based on the percentage of syringes used, specifically it will be calculated as follows:

$$\text{Study drug adherence for each visit} = \frac{[(\text{no. of syringes dispensed} - \text{no. of syringes returned}) / (\text{no. of weeks between the 2 consecutive visits})] * 100\%.$$

A patient will be considered adherent for each visit interval if he/she uses at least 75% of the study drug syringes dispensed for that interval.

Treatment adherence will be listed and summarized using the ITT population. The number and proportion of patients who are compliant at each visit by treatment group will be summarized and compared using a Chi-square test unless the total count is <10.

The overall adherence during the study will be calculated for each patient. This will be calculated by taking the number of visits the patient was compliant divided by the total number of visits with nonmissing adherence data for this patient (that is, the proportion of visits at which the patient was compliant among visits with non-missing adherence data for the patient). The overall adherence will be summarized and presented in descriptive statistics that include the sample size, mean, median, 10th and 90th percentiles, and standard deviation. The overall adherence will be used as one of the factors when determining if a patient is eligible for the PP population.

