4.13.4. Sensitivity Analyses of Primary Endpoint

The time-to-event analysis for the primary endpoint will be repeated using the PP population, but NNT will not be calculated.

Randomization was stratified by site. To account for the stratification, a time-to-event analysis of the primary endpoint stratified by site will be performed as a sensitivity analysis.

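### Per-protocol membership is judged over the whole study, so an on-drug MI or stroke can be deleted because of what follows it, and the per-protocol hazard ratio can be biased in either direction

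*SAP*

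**What the plan says.** SAP 4.5, Table 4.1 (matched by Protocol Table GBDJ.1) takes the ITT population and keeps those who "have not permanently discontinued study drug", who "have completed the study", who "have an overall adherence with study drug of" at least 75%, and who have no important protocol deviation. SAP 4.2 words the completion condition differently: the set is "defined as all randomized patients who have not permanently discontinued study drug, discontinued from the study", with the same adherence and deviation conditions.

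Two other sections fix the time window. In SAP 4.11, "The overall adherence during the study will be calculated for each patient", as the share of adherent visits among all visits with adherence data. SAP 4.7 lists important deviations without a time limit, including "unblinding of treatment assignment for any reason", incorrect dispensation, prohibited medication, and safety measures missed for 18 months or more while on drug.

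SAP 4.13.4 then states: "The time-to-event analysis for the primary endpoint will be repeated using the PP population, but NNT will not be calculated". The PP set is also used for stroke subtypes (SAP 4.14.3). The primary analysis itself is ITT (SAP 4.13).

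**The concern.** In a time-to-first-event analysis a patient's contribution ends at the first event. Here, membership of the analysis set can be decided by what happens later. Take a fully adherent patient with an adjudicated MI in year 2 whose attending physician then asks that study drug be stopped for good, a route named in Protocol 8.3.3. The patient was on drug and adherent for the whole time at risk, yet both patient and event leave the PP analysis.

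The reverse loss also occurs. A patient who takes drug for four years, stops, and never has an event contributes nothing, instead of four years of on-drug follow-up.

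At stake is whether the PP hazard ratio can be read as a check on the primary result. The only other analysis in SAP 4.13.4 is stratification by site, which does not address adherence.

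**Working it through.** **Plan figures that can be checked.** The documents give no PP event count and no rate of study-drug discontinuation. The nearest relevant figure is the synopsis count of 9500 completers out of 9600 randomized. With 0.15% annual dropout (SAP 4.1) and about 6.5 years average follow-up (Protocol 7.1), 9600 × 0.0015 × 6.5 = 93.6, leaving about 9506. The planned completers are therefore randomized patients minus dropouts, with nothing deducted for deaths. SAP 4.2 excludes only those who discontinued from the study, and SAP 4.3.4.3 and 4.12 list death apart from early discontinuation. Deaths are kept in everything below.

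**Inputs.** From the documents: placebo event rate 2%/y, and follow-up from 5.6 years with an average of about 6.5 years. Assumed, because the documents are silent:
- 30% or 50% of first events are fatal (f);
- background permanent drug stopping is b per year;
- a proportion q of patients with a nonfatal first event stop drug because of it;
- follow-up is spread over 5.6 to 7.7 years.

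**Who is retained.** An event-free patient must stay on drug to the end, with probability exp(−bT). A nonfatal-event patient must do the same and also not stop because of the event: (1 − q)·exp(−bT). A patient with a fatal first event need only be on drug until death, at about T/2 on average: exp(−bT/2). Retention of event patients relative to event-free patients is therefore about

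R = f·exp(bT/2) + (1 − f)(1 − q),

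and the PP hazard ratio is about the true hazard ratio × R(dulaglutide)/R(placebo). With T = 6.5, exp(bT/2) is 1.139, 1.215 and 1.297 for b = 4%, 6% and 8%/y.

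**Results at a true hazard ratio of 1.00.** The last column is from simulation with 2 million patients per arm.

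| b, placebo/dulaglutide | q, placebo/dulaglutide | f | R placebo | R dulaglutide | Ratio | Simulated |
|---|---|---|---|---|---|---|
| 4%/4% | 20%/30% | 0.3 | 0.902 | 0.832 | 0.92 | 0.92–0.95 |
| 4%/4% | 20%/30% | 0.5 | 0.969 | 0.919 | 0.95 | same range |
| 4%/4% | 30%/20% | 0.3 | 0.832 | 0.902 | 1.08 | 1.05–1.09 |
| 4%/4% | 30%/20% | 0.5 | 0.919 | 0.969 | 1.05 | same range |
| 4%/6% | 20%/20% | 0.3 | 0.902 | 0.925 | 1.03 | 1.03–1.09 |
| 4%/8% | 20%/20% | 0.5 | 0.969 | 1.048 | 1.08 | same range |
| 4%/4% | 20%/20% | 0.3 | 0.902 | 0.902 | 1.00 | 0.999 |

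At a true hazard ratio of 0.82, the first scenario (20% against 30% post-event stopping) gives a simulated 0.76 to 0.78.

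**Events lost.** In the runs with unequal post-event stopping, about 13% to 24% of first events per arm occurred on drug and were still dropped. In the fully balanced run (last row) the hazard ratio is right, but 21% of on-drug first events are lost in each arm.

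**After the fix.** Censoring at drug stop, with status judged only up to the first event, matched the ITT estimate to within 0.002 in every run of the 20%/30% comparison and its reverse. This follows from assuming that background stopping is independent of risk.

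**The case against.** The best counter-argument is that this is a supportive analysis, that PP sets are often defined this way, and that nothing shows post-event stopping will differ by arm. MI and stroke are not among the listed reasons for permanent discontinuation in Protocol 8.3.3. Protocol 8.3.2 asks for every effort to restart drug, and a temporary stop does not remove a patient. With equal rates the hazard ratio is nearly right. All of this stands, and it limits the size of the problem. It does not justify selecting patients on what happens after the outcome.

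Second, the protocol already plans an on-drug analysis. Protocol 12.2.1 commits to an as-treated analysis of primary events occurring on study drug, which would retain the MI in the example. The SAP does not carry it forward, and its revision history records no decision to drop it. So it cannot be said that no on-drug analysis was ever planned, only that the SAP does not specify one.

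Three stronger readings are tempting, and the documents do not support them:
- *Every CV death is excluded.* The completion wording in Table 4.1 could be read that way, but SAP 4.2 and the 9500 planned completers point the other way. What remains is a missing sentence. One narrow route does exist on a literal reading: a death judged serious, unexpected and possibly related is unblinded to the sponsor's safety group and the CRO (SAP 5.5.1), and unblinding for any reason is an important deviation.
- *The PP result will favor dulaglutide.* Gastrointestinal events, the most common adverse events on the drug (Protocol 5.3), would most naturally raise background stopping. With equal post-event stopping, that pushes a null result to about 1.03 to 1.09, against the drug.
- *The noninferiority conclusion is compromised.* The 1.3-margin test rests on the adjusted interval from the ITT analysis. No PP noninferiority test is planned.

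**Conclusion.** The flaw is one of definition, and it is certain on the text: no PP criterion ends at the first primary event, so following the plan as written deletes some on-drug MIs and strokes because of their aftermath and discards the on-drug time of patients who stop early. Whether this biases the PP hazard ratio depends on how retention of event patients relative to event-free patients compares between arms. The documents fix neither the size nor the direction.

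The illustrations run from about 0.92 to about 1.09 for a null drug. They rest on the assumed fatal share, background stopping of 4% to 8%/y and post-event stopping of 20% to 30%. The ITT primary test, alpha and power are not affected. The point is worth correcting because, as the SAP stands, this is the only adherence-based check on the primary endpoint in 4.13.4.

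**What to change.** Revise SAP 4.2, Table 4.1, 4.7 and 4.13.4, with matching wording in Protocol Table GBDJ.1:

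1. Exclude patients from the PP set only for eligibility deviations present at randomization.
2. Apply every post-randomization criterion only up to the first primary event: permanent drug stop, study withdrawal, adherence below 75%, and all post-randomization deviations in SAP 4.7 (incorrect dispensation, unblinding, prohibited medication, missed safety measures).
3. Censor event-free patients on the date a criterion is first met, instead of deleting them.
4. State that death counts as completing the study, and align Table 4.1 with SAP 4.2.
5. Carry the as-treated analysis of Protocol 12.2.1 into SAP 4.13.4.

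One detail must be written down. Overall adherence becomes a running proportion of visits, so a single poor first interval would put a patient at 0%. The SAP should say how many visits are needed before the 75% rule applies.

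The cost is SAP wording and programming; Protocol 8.3.3 already requires the drug-stop date to be documented. The downside is that censoring at drug stop can itself be informative if patients who stop differ in risk, so the analysis stays supportive.

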4.6. Patient Disposition

A listing of patient discontinuations will be presented for all randomized patients. Summary analyses will be conducted for the ITT and PP populations.

Number and proportions of patients will be presented for each treatment group and compared across treatment groups using a Chi-square test or Fisher's exact test.

4.7. Important Protocol Deviations

Important protocol deviations will be listed for all randomized patients. The following protocol deviations will be considered important:

- not meeting any of the inclusion criteria [1], [6], and [9], or meeting any of the exclusion criteria [10], [11], [12], [13], and [21] (REWIND study protocol) that affect the primary endpoint analysis
- nonadherence to treatment regimen (that is, overall treatment adherence <75%)
- incorrect dispensation of study drug (patient received incorrect treatment)
- unblinding of treatment assignment for any reason
- using prohibited concomitant medications (that is, non-study GLP-1 analogs, pramlintide, or prescription weight loss drugs)
- safety laboratory or measures (calcitonin and/or serum creatinine and/or ECG) not taken for 18 or more months and study drug not discontinued

4.8. Patient Characteristics at Baseline

Demographic and baseline characteristics will be summarized by treatment group using ITT and PP populations. For continuous measures, summary statistics will include sample size, mean, median, 10th percentile, 90th percentile, and standard deviations. Mean will be analyzed using ANOVA. For categorical measures, summary statistics will include sample size, number, and proportion. Treatment group comparisons will be performed using a Chi-square test or Fisher's exact test.

4.9. Concomitant Medications

Concomitant medications will be summarized by different categories and treatment group using ITT population. All concomitant therapies originally mapped using the WHODRUG dictionary in the clinical trial database will be further classified using Anatomical Therapeutic Chemical (ATC) code for reporting purpose. The number and proportion of patients will be analyzed using a Chi-square test or Fisher's exact test.

4.10. Historical Illnesses at Visit 1

A limited number of historical illnesses collected at Visit 1 will be listed using all randomized patients. Summary reports will be conducted by treatment group using the ITT population. Historical illnesses will be reported using the terms in the medical history questions on the case report forms. The number and proportion of patients will be analyzed using a Chi-square test or Fisher's exact test.

4.11. Treatment Adherence

Treatment adherence will be assessed for each visit interval. Patients will be instructed to return any unused study drug syringes at each study visit for the purposes of study drug accountability. Study drug adherence will be calculated at each visit after baseline when study drug is dispensed based on the percentage of syringes used, specifically it will be calculated as follows:

$$\text{Study drug adherence for each visit} = \frac{[(\text{no. of syringes dispensed} - \text{no. of syringes returned}) / (\text{no. of weeks between the 2 consecutive visits})] * 100\%.$$

A patient will be considered adherent for each visit interval if he/she uses at least 75% of the study drug syringes dispensed for that interval.

Treatment adherence will be listed and summarized using the ITT population. The number and proportion of patients who are compliant at each visit by treatment group will be summarized and compared using a Chi-square test unless the total count is <10.

The overall adherence during the study will be calculated for each patient. This will be calculated by taking the number of visits the patient was compliant divided by the total number of visits with nonmissing adherence data for this patient (that is, the proportion of visits at which the patient was compliant among visits with non-missing adherence data for the patient). The overall adherence will be summarized and presented in descriptive statistics that include the sample size, mean, median, 10th and 90th percentiles, and standard deviation. The overall adherence will be used as one of the factors when determining if a patient is eligible for the PP population.

4.12. Treatment Exposure and Study Duration

Patients may discontinue study treatment but remain in the study.

Treatment exposure will be defined as the total duration of time that the patient is believed to be taking study drug. This time period will be derived by subtracting the randomization date (Visit 3) minus 1 day from the last visit date for patients actively participating in the study at the time of database lock (at the conclusion of REWIND) or the discontinuation date for patients who discontinue study drug. The duration of treatment exposure will be reported in months and will be compared between treatments using nonparametric methods (Wilcoxon rank-sum tests). The duration of treatment exposure will be summarized by treatment group using the ITT population. The duration of exposure will be categorized into the following groups: ≥ 2 weeks, ≥ 3 months (13 weeks), ≥ 6 months (26 weeks), ≥ 1 year (52 weeks), ≥ 2 years, ≥ 3 years, ≥ 4 years and ≥ 5 years, etc. These categories will be summarized by the number and proportion of patients in each category by treatment group.

Keeping with the ITT principle, the study duration for a patient will commence on the date of randomization to the time of last participation in the study. This will be the patient's safety reporting period. At the time of datalock (at the conclusion of REWIND), the time of last participation will be the Final Visit date for patients still actively participating in the study; the

date of discontinuation if the patient discontinued from the study early; or the date of death if the patient dies during the study. The study duration will be reported in months and will be compared between treatments using nonparametric methods (Wilcoxon rank-sum tests). In addition, a categorical breakdown of the study duration will be provided using the same categories as the duration of treatment exposure.

The number and proportion of patients who discontinue study drug will be compared between treatment groups with separate analyses for the reasons for the discontinuation, (for example, AE, protocol, or patient decision). The length of time patients are off study drug will be summarized by treatment group. The analyses for discontinuations will also be performed by visit.

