### **8.3.2. Temporary Discontinuation of Study Drug**

After randomization, the investigator may need to temporarily discontinue study drug, for example, due to an AE or a clinically significant laboratory value. If study drug discontinuation is due to an AE, the event is to be followed according to the procedures in Section 10.2 of this protocol and documented. Investigators should inform the CRO that study drug has been temporarily discontinued. Every effort should be made by the investigator to maintain patients on study drug and to restart study drug promptly after any temporary discontinuation, as soon as it is safe to do so. The patient will remain in the study to be evaluated for efficacy and safety endpoints and monitored for all visits and testing. The dates of study drug discontinuation and restart will be documented.

If a woman of childbearing potential becomes pregnant after randomization, study drug should be temporarily discontinued. The patient will remain in the study to be evaluated for efficacy and safety endpoints and monitored for all visits and testing. Study drug may be resumed after the pregnancy but not until it is safe to do so.

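### SAP 4.12 does not net temporary interruptions out of treatment exposure, and SAP 4.11 does not say how they count towards adherence and per-protocol membership

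*SAP*

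**What the plan says.** **Exposure.** SAP 4.12 gives a definition and a derivation. The definition is: "Treatment exposure will be defined as the total duration of time that the patient is believed to be taking study drug". The derivation has two branches: "This time period will be derived by subtracting the randomization date (Visit 3) minus 1 day from the last visit date for patients" still taking part at database lock, "or the discontinuation date for patients who discontinue study drug". The result is put into duration categories and compared between arms by a Wilcoxon rank-sum test. The same section adds: "The length of time patients are off study drug will be summarized by treatment group".

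**Adherence.** SAP 4.11 states: "Study drug adherence will be calculated at each visit after baseline when study drug is dispensed based on the percentage of syringes used". The percentage is syringes dispensed minus syringes returned, divided by the weeks between visits. An interval is adherent if at least 75% of the syringes dispensed for it were used. Overall adherence is then "the proportion of visits at which the patient was compliant among visits with non-missing adherence data". Protocol 9.9 uses the same approach.

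**Per-protocol set.** SAP 4.2 and SAP Table 4.1 remove patients who stopped drug permanently and require overall adherence of at least 75%. SAP 4.7 makes overall adherence below 75% an important deviation. Protocol Table GBDJ.1 matches the SAP, but the running text of Protocol 12.2.1 does not limit the discontinuation criterion to permanent stops.

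**Temporary stops.** Protocol 8.3.2 asks for a prompt restart once safe but sets no maximum length. It also says: "The dates of study drug discontinuation and restart will be documented".

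**The concern.** The definition in SAP 4.12 describes time on drug. Both derivation branches measure calendar time to one end date. A patient who stops, restarts and is still attending at lock fits the description of both branches, and neither gives time on drug.

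The adherence rule has a related gap. Nothing says what happens to an interval in which no drug was dispensed because of an interruption. It could drop out of the denominator or count as zero. The choice decides whether a patient with a long interruption is in the per-protocol set, because the SAP does not exclude temporary stops in any other way, and the deviation in SAP 4.7 uses the same adherence figure.

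This matters for interpretation. Protocol 7.3 describes adherence as critical in this intent-to-treat trial. If superiority fails, noninferiority is tested against a margin of 1.3 (SAP 4.13.2), and time off drug tends to pull the arms together. Readers would then turn to exposure, adherence and the per-protocol repeat of the primary analysis (SAP 4.13.4). An imbalance between arms is plausible, though not shown: Protocol 5.3 names gastrointestinal events as the most common adverse events on dulaglutide, and Protocol 7.1.4 allows patients who cannot tolerate the drug to stop temporarily.

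**Working it through.** The documents give no figure on this point to reproduce, so the check applies the SAP rules to an assumed patient.

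**Inputs from the documents**
- Follow-up: 6.5 years = 78 months (average follow-up, Protocol Synopsis).
- Dispensing every 3 months (Protocol 7.1.4.1): 78 / 3 = 26 intervals of about 13 weeks.
- Unused syringes are returned at each visit (Protocol 7.1.4.1), so a stop between visits lowers that interval's percentage.
- Per-protocol cut: 75% (SAP Table 4.1).

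**Assumptions:** drug stopped for 36 months from month 24, then restarted; full use whenever on drug. The one-day term in the derivation is ignored.

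**Exposure**
- On drug: 78 - 36 = 42 months.
- Last-visit branch: 78 months, too high by 36 months (36 / 42 = 86%).
- Discontinuation-date branch: 24 months, too low by 42 - 24 = 18 months (18 / 42 = 43%).
- If the off-drug summary includes temporary gaps, the last-visit branch shows 78 + 36 = 114 months for a patient followed for 78.

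**Overall adherence** = adherent intervals / scored intervals. Reading A treats an undispensed interval as missing. Reading B applies the formula literally: (0 - 0) / 13 weeks = 0%.

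For a stop at a visit, 8 intervals precede the gap, 12 fall in it and 6 follow it. For a mid-interval stop (month 25.5, restart at month 61.5), the interval containing the stop is about 50% used and so non-adherent, and 13 intervals remain adherent.

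| Gap | Stop falls | Reading A | Reading B |
|---|---|---|---|
| 36 months from month 24 | at a visit | 14/14 = 100% | 14/26 = 53.8% |
| 36 months from month 24 | mid-interval | 13/14 = 92.9% | 13/26 = 50.0% |
| 60 months from month 12 | at a visit | 6/6 = 100% | 6/26 = 23.1% |
| 60 months from month 12 | mid-interval | 5/6 = 83.3% | 5/26 = 19.2% |

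Every Reading A value passes 75% and every Reading B value fails. With 6-month dispensing and a stop at a visit, the 36-month gap gives 7/7 = 100% or 7/13 = 53.8%, the same split.

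Reading B does not exclude short interruptions. A gap of 18 months starting at a visit still passes (20/26 = 76.9%); 21 months fails (19/26 = 73.1%).

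**Effect on an arm mean, last-visit branch only.** The documents give no interruption rates. If 5% to 20% of an arm accumulates 1 to 3 years off drug, mean exposure is overstated by 0.05 x 1 = 0.05 y to 0.20 x 3 = 0.6 y, that is 0.8% to 9.2% of 6.5 y. On the other branch the error has the opposite sign.

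**The case against.** The strongest defence is that time off drug is not hidden. SAP 4.12 summarizes its length by arm, and Protocol 12.2.9.1 compares temporary discontinuations by arm and reason and counts them as one, two, or three or more. That stands as a real mitigation. But it is a separate table and leaves the exposure variable, its categories and its Wilcoxon test unchanged.

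A reader might infer something stronger: that a patient who interrupts at month 6 and never restarts will be reported as exposed for 6.5 years, fully adherent and per-protocol. The documents do not support this.
- The discontinuation-date branch is not limited to permanent stops. Applied here it gives 0.5 years, which agrees with the SAP's definition.
- Unused syringes come back at each visit, so a stop between visits normally adds a non-adherent interval. A stop midway through months 3-6 gives 1/2 = 50%, and one midway through months 6-9 gives 2/3 = 66.7%, even if all later intervals are missing. Both fail 75%.
- Dropping undispensed intervals is only one reading of SAP 4.11.

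Nor can one infer that exposure is always overstated: for a patient who restarts, the error goes up or down with the branch.

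It is also fair to say that measuring adherence only while drug is supplied, with persistence reported separately, is a legitimate choice. Scoring permanent stoppers as 0% in the intent-to-treat adherence summary would be a preference, and it is not asked for here. Finally, the text of Protocol 12.2.1, read literally, would remove any discontinuer from the per-protocol set. That adds a third version of the rule and does not settle the question.

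**Conclusion.** The concern holds for patients who stop and restart. The exposure derivation contradicts its own definition, and both branches give a wrong answer: 78 or 24 months against 42 in the example. The categories and the between-arm test carry that error. Separately, overall adherence for the same patient is 93-100% or 50-54% depending on an unstated scoring rule, so two programmers could place the patient on opposite sides of the per-protocol cut.

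The consequence is confined to exposure reporting, adherence figures and the per-protocol sensitivity analysis. The primary intent-to-treat analysis does not use any of these quantities and is unaffected. How many patients are involved cannot be told from the documents; the gap lengths, their timing and the interruption rates above are all assumptions. This is worth correcting before unblinding because per-protocol membership depends on it, but it does not threaten the trial's main conclusion.

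**What to change.** 1. **SAP 4.12.** Derive exposure as randomization to last dose or last visit, minus the sum of documented temporary off-drug periods. Treat an interruption still open at last participation as ending exposure at its start date. This is an analysis derivation only and changes no clinical rule.
2. **SAP 4.11.** State how an interval with no drug dispensed is scored. For per-protocol membership, count intervals undispensed because of a temporary interruption as 0% adherent.
3. **Per-protocol definition.** Reconcile the text of Protocol 12.2.1 with Protocol Table GBDJ.1, SAP 4.2 and SAP Table 4.1 on whether temporary discontinuation excludes a patient.

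The cost is SAP wording and somewhat more derivation work. Protocol 8.3.2 already requires stop and restart dates to be documented, but it does not say they are captured on the case report form, so that should be confirmed. The reported exposure may become less favourable and the per-protocol set smaller.
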